2. Measure vital signs, including respiratory rate (breaths per minute), body temperature (F), blood pressure (mm Hg), pulse rate (beats per minute), oxygen saturation (%), and weight measurement (lb. or kg).
3. Physical examination by Principal Investigator.
4. Collection of laboratory samples - Comprehensive Metabolic Panel (CMP), Complete Blood Count (CBC), Coagulation Panel, and Urine pregnancy test if female of childbearing potential.
5. Completion of patient questionnaire including Visual Analog Scale of Symptoms, Fatigue scale, and SF-36 and PHQ-9.
6. Assess the incidence of any adverse event since the last visit.

Unscheduled Visits

At his/her discretion, the Investigator may arrange for a study participant to have an unscheduled visit (UNS). Some of the circumstances by which a study participant will be called for a UNS visit are:

- Adverse events (AEs) that require follow-up.
- Collection of laboratory samples for safety reasons.
- Procedures missed at previous study visits. Procedures refer to laboratory, test, and assessments. Even though a missing process is deemed a protocol violation, we included this example in the unscheduled visit to act as a reference.

All unscheduled visits should be documented in the study's participant source.

Trial Assessments

Assessments Related to Endpoints

Visual Analog Scale of Symptoms

Visual analog scales (VAS) are psychometric measuring instruments used to document the characteristics of disease-related symptom severity in individual patients. Another objective of this scale is to achieve a rapid (statistically measurable and reproducible) classification of symptom severity and disease control in a population of patients (Klimek et al., 2017).

On a scale from zero to ten centimeters, we aim to assess neurological and non-neurological symptoms in this clinical trial, with zero representing no symptoms and ten describing the worst symptoms possible.

Table 2: VAS of symptoms.

Neurological Symptoms	Non-Neurological Symptoms
1. Extreme fatigue	1. Dyspnea
2. Headache	2. Cough
3. Sleep issues	3. Body Aches
4. Brain fog	4. Joint pain
5. Loss of Taste/Smell	

Fatigue Assessment Scale (FAS)

The FAS is a ten-item scale that assesses the symptoms of chronic fatigue in an individual. The FAS considers fatigue as a unidimensional concept rather than a collection of variables that may be measured separately. Additionally, to guarantee that the scale would assess all elements of fatigue, the scale's developers included questions that represented both physical and mental symptoms of the disease (Michielsen et al., 2004).

Short Form Questionnaire – 36

The SF-36 is a multi-purpose survey intended to collect adult patients' views of their health and well-being. In all, there are 36 questions on the SF-36, which are organized into eight dimensions: physical functioning, physical and emotional limitations, social functioning, physiological discomfort, general and mental health. It is a more public health measure than targeted at a particular age group, illness, or treatment group. This questionnaire may be given in various situations (e.g., primary care, community clinics, specialty care serving patients with chronic conditions). It has been extensively utilized and proved helpful in multiple studies of general and populations throughout the years, including evaluating the relative burden of illnesses and differentiating the health benefits provided by a range of various therapies (National Center for Interprofessional Practice and Education, 2016).

Physical Examinations

The principal investigator or delegated sub-investigator will perform a complete physical examination. This exam will include general appearance, head, eyes, ear, nose, and throat (HEENT), neck, cardiovascular, thorax/lungs, abdomen, genitourinary, musculoskeletal, lymph nodes, skin, neurological and mental status examination, height (at Screening only), and body weight at Visits 1, 2, 3, 4, 5, 6, 7 and 8.

The principal investigator or delegated sub-investigator will evaluate the clinical significance of abnormal findings identified during physical examinations. Pre-existing conditions diagnosed through assessments and examinations at the screening visit or during the screening period are not adverse events but are recorded as medical history. If any clinically significant abnormal findings are

discovered after informed consent or any pre-existing conditions worsen during the trial, these must be recorded as adverse events.

Vital Signs

Vital signs will be measured at Visits 1, 2, 3, 4, 5, 6, 7 and 8. Study personnel will measure respiratory rate (breaths per minute), pulse rate (beats per minute), blood pressure (mmHg) (measured after the study participant has been seated for more than 5 minutes of rest), body temperature (F), and oxygen saturation (%). The principal investigator must evaluate the clinical significance of any abnormal result. Clinically significant abnormal findings will be reported as adverse events.

Clinical Safety Laboratory Parameters

The following laboratory parameters should be collected at Visit 1, 2, 5, and 8.

- Comprehensive Metabolic Panel, also known as CMP or Chemistry Panel, is a group of different tests that measure several substances in the study's participant blood. The following tests are included in this panel:

Comprehensive Metabolic Panel (CMP)	Reference Range	Units
GLUCOSE	70-99	MG/DL
BUN	6-20	MG/DL
CREATININE	0.60-1.30	MG/DL
eGFR AFRICAN AMER.	>60	ML/MIN/1.73
eGFR NON-AFRICAN AMER.	>60	ML/MIN/1.73
CALC BUN/CREAT	6-28	Ratio
SODIUM	133-146	MEQ/L
POTASSIUM	3.5-5.4	MEQ/L
CHLORIDE	95-107	MEQ/L
CARBON DIOXIDE	19-31	MEQ/L
CALCIUM	8.5-10.5	MG/DL
PROTEIN, TOTAL	6.1-8.3	G/DL
ALBUMIN	3.5-5.2	G/DL
CALC GLOBULIN	1.9-3.7	G/DL
CALC A/G RATIO	1.0-2.6	Ratio
BILIRUBIN, TOTAL	<=1.2	MG/DL
ALKALINE PHOSPHATASE	40-114	U/L
AST	9-40	U/L
ALT	5-40	U/L

- Complete Blood Count, also known as CBC, hemogram, or CBC with Differential, is a group of tests that evaluate the cells circulating in the blood. The following tests are included in this panel:

CBC with manual differential	Reference Range	Units
WBC	3.5-11.0	K/UL
RBC	3.80-5.40	M/UL
HEMOGLOBIN	11.5-15.5	G/DL
HEMATOCRIT	34.0-45.0	%
MCV	80.0-99.0	fL
MCH	25.0-33.0	PG
MCHC	31.0-36.0	G/DL
RDW	11.5-15.0	%
NEUTROPHILS	40.0-75.0	%
LYMPHOCYTES	20.0-45.0	%
MONOCYTES	4.0-12.0	%
EOSINOPHILS	0.0-7.0	%
BASOPHILS	0.0-2.0	%
PLATELET COUNT	130-400	K/UL
ABSOLUTE NEUTROPHILS	1.50-7.50	K/UL
ABSOLUTE LYMPHOCYTES	1.00-4.00	K/UL
ABSOLUTE MONOCYTES	0.20-1.00	K/UL
ABSOLUTE EOSINOPHILS	0.00-0.50	K/UL
ABSOLUTE BASOPHILS	0.00-0.20	K/UL

- Coagulation Tests including Prothrombin Time (PT, PTT-INR) to identify any coagulation disorder during study participation.

Coagulation	Reference Range	Units
Prothrombin Time (PT)	12.5-14.7	Seconds
INR	2.0-3.0	N/A
Partial thromboplastin time (PTT)	25.2-40.0	Seconds

- Urine Pregnancy Test, a urine sample, preferably collected during morning time, to confirm pregnancy during study participation. This test will be limited to Women of Childbearing Potential (WOCBP).

Pregnancy Test	Reference Range	Units
Urine Pregnancy Test	Positive - Negative	N/A

PHQ-9

The PHQ-9 is a depression module, which scores each of the nine DSM-IV criteria as "0" (not at all) to "3" (nearly every day). It is not a screening tool for depression, but it is used to monitor the severity

of depression. In addition to making criteria-based diagnosis of depressive disorders, the PHQ-9 is also a reliable and valid measure of depression severity.

When doing this evaluation, if a study subject is identified as having depression and is not actively managed by a behavioral health professional or physician, the subject will be advised to seek appropriate treatment and management of depression. The principal investigator will follow up with the subject to confirm that he or she has received proper treatment.

In addition, if a subject has suicidal ideation (SI) and/ or homicidal ideation (HI), the emergency response system will be activated by calling 911 and arranging for the subject to be immediately evaluated for risk at the nearest emergency department.

Other Assessments

Demography

Demographic data will be collected at the Screening Visit, including age, race, ethnicity, date of birth, and gender.

Medical and Surgical History

The medical information on any previous concomitant illnesses other than Chronic Post-COVID19 Syndrome should be collected during Screening Visit and updated if needed during the subsequent study visits. For planned procedures/hospitalizations during the clinical trial, documentation should be completed at the screening time.

Chronic Post-COVID-19 Syndrome and Previous Therapy for this disease

The date of diagnosis of Chronic Post-COVID-19 Syndrome and previous treatments will be recorded during the Screening visit.

Concomitant Medication Review

Data concerning concomitant medications and procedures will be collected throughout the clinical trial. This data will be obtained at scheduled or unscheduled visits based on information provided by the patient.

Handling of Biological Samples

Sampling tubes, material for shipments of the samples, and a laboratory manual detailing all sample collection and shipment procedures will be provided and distributed to the clinical trial site by the selected laboratory. Laboratory samples will be collected as per protocol during Visit 1 – Screening or Visit 2 – Infusion 1 (Baseline), Visit 5 – Infusion 4, and Visit 8 - End of Study.

Adverse Events

Unanticipated Problems Involving Risk to Subjects or Others

Any incident, experience, or outcome that meets all the following criteria:

- Unexpected in nature, severity, or frequency (i.e., not described in study-related documents such as the IRB-approved protocol or consent form, the investigator's brochure, etc.)
- Related or possibly related to participation in the research (i.e., perhaps related means there is a reasonable possibility that the incident experience or outcome may have been caused by the procedures involved in the study.
- Serious (as defined below) ***“Serious” is different than “severe” as reported in the CTC criteria that apply a grade to the AE.***

Adverse Event

An **adverse event** (AE) is any symptom, sign, illness, or experience that develops or worsens in severity during the study. Intercurrent illnesses or injuries should be regarded as adverse events.

Abnormal results of diagnostic procedures are adverse events if the abnormality:

- results in study withdrawal
- is associated with a serious adverse event
- is associated with clinical signs or symptoms
- leads to additional treatment or to further diagnostic tests
- is considered by the investigator to be of clinical significance

Serious Adverse Event

Adverse events are classified as serious or non-serious. A **serious adverse event** is any AE that is:

- fatal
- life-threatening
- requires or prolongs hospital stay
- results in persistent or significant disability or incapacity
- a congenital anomaly or congenital disability
- an important medical event

Important medical events are those that may not be immediately life-threatening but are clearly of major clinical significance. They may jeopardize the subject and require intervention to prevent the other serious outcomes noted above. For example, drug overdose or abuse, a seizure that did not result in an in-patient hospitalization, or intensive treatment of bronchospasm in an emergency department would typically be considered serious.

All adverse events that do not meet any of the criteria for serious should be regarded as *nonserious adverse events*.

Adverse Event Reporting Period

The study period during which adverse events must be reported is typically defined as the period from the initiation of any study procedures to the end of the study treatment follow-up. For this study, treatment follow-up is described as approximately 16 weeks following the last administration of study treatment.

Stopping Rules

Infusion Stopping Rules

Study treatment infusion will be stopped if a least one of the following events occurs:

1. Allergic reaction as evidenced by severe dyspnea (defined as intense tightening of the chest, air hunger, breathlessness or feeling of suffocation), bronchospasm (defined as coughing, wheezing, difficulty breathing) or hypoxia (defined as pulse oximeter reading of less than 90%) after the product has been administered intravenously.
2. Hypersensitivity reactions such as rash, urticaria, itching, angioedema, nausea, vomiting, hypotension, or any evidence of anaphylaxis.
3. The patient verbally declines the treatment at any moment prior, or during the infusion.
4. Any febrile reaction will be an indicator for pausing the infusion for further evaluation.
5. Malignant Systolic blood pressure (SBP) greater than 170 and/or diastolic blood pressure greater than 100. SBP less than 80mm/Hg and/or DBP less than 40mm/Hg. *
6. Sudden Severe Hypotension (40 mm/Hg drop from infusion starting baseline) or systolic blood pressure <80mmHg.
7. Respiratory distress defined as having an acute sudden onset of shortness of breath or increased work of breathing, SaO₂ less than 90% or a respiratory rate >22 or < 10 breaths per minute. Any increased oxygen support that could indicate imminent respiratory failure.
8. Sudden increase or decrease in pulse rate of 30 bpm or more from infusion starting baseline or an absolute tachycardia of greater than 140 bpm or absolute bradycardia less than 45 bpm.
9. Change in neurologic status from infusion starting baseline including alertness.
10. The Principal Investigator may stop the infusion at any time, based upon PI's discretion.

*Any blood pressure from baseline exceeding or falling below $\pm 20\%$ of baseline or $\geq 140/90$ will necessitate a pause for evaluation.

Suppose an infusion is stopped for a subject due to an adverse event or serious adverse event, including but not limited to hypersensitivity reaction/anaphylaxis. In that case, no additional study treatment will be given to the study participant who develops the event. Although the study participant will not

receive the investigational product, he or she must be followed for safety purposes according to the protocol.

Study Stopping Rules

This Clinical Trial will stop if any of the following events are present:

1. Subject's Death.
2. Any thromboembolic event will cause a pause in the study until an evaluation can be done by the DSMB, Principal Investigator and Medical Monitor to determine relationship.
3. Any cerebrovascular ischemia or seizure event occurring within 72 hours after any of the investigational product administrations.
4. Any Serious Adverse Events of the following:
 - When there is one CTCAE.v5 grade 4 or 5 AE, irrespective of attribution.
 - Either any CTCAE Grade 2 adverse event that persists for more than two weeks or any Grade 3 adverse event that occurs within 72 hours after product administration.

Should the study participant discontinue study treatment, he/she will be followed for safety according to the protocol safety monitoring plan. The study participant will receive follow-up communication via phone calls or electronically to ascertain the outcome until resolved fully. All will be documented as per protocol.

FDA shall review all changes to the study-stopping rules. If the study is suspended for any reason, it will not be re-opened until FDA agrees. Whether the study is stopped or suspended, all subjects will be followed to the EOS visit.

Statistical Methods

The sample size consists of 80 subjects who have been diagnosed with Chronic Post-COVID-19 Syndrome. All data collected from subjects who are enrolled and received the investigational product will be analyzed. The incidence of Adverse Events and Serious Adverse Events will be recorded and reported. Efficacy will be measured by improving the subject's signs and symptoms associated with Chronic Post-COVID-19 Syndrome. Interim analysis of all safety and efficacy data may be performed at any time deemed appropriate by the Sponsor. Data may be analyzed for internal informational purposes, reports, presentations, and manuscripts.

A repeated measure mixed model will be used to assess within-subject changes from baseline. Correction for multiple comparisons will be employed for post-hoc comparisons. Chronic Post COVID-19 Syndrome's assessments (VAS, FAS, PHQ-9, and SF-36) at infusion 1 (before treatment) will be utilized as a baseline.

Data Handling

Case Report Forms (CRF)

As used in this protocol, the term CRF should be understood to refer to either a paper form or an electronic data record, or both. Reports received by the site, or the central laboratory should be printed, retained as source documentation, and signed by the principal investigator, indicating which values are considered clinically significant and reported as AEs if applicable.

The completion, review, and approval of all CRFs and the completeness and authenticity of all clinical and laboratory data entered on these CRFs are always the Principal Investigator's responsibility. The signature of the Principal Investigator will be required to attest that the information contained on the CRFs is accurate.

Changes in the Conduct of the Clinical Trial

Protocol Amendments

Any change to the protocol will need to have a protocol amendment submitted to the IND, and FDA and IRB must agree before proceeding.

Premature Clinical Trial Termination

Both the Study Investigator and Sponsor have the right to terminate the clinical trial at any time. Should this become necessary, the procedures will be agreed upon after consultation between the two parties. In terminating the clinical trial, the Sponsor and the Study Investigator will ensure that adequate consideration is given to protect the best interests of the study participants. Regulatory authorities and IRB will be informed.

In addition, the Sponsor reserves the right to terminate the participation of any clinical trial site. Conditions that may warrant termination include, but are not limited to:

- Insufficient adherence to protocol requirements
- Failure to enter patients at an acceptable rate
-

Reporting and Publication

Neither the complete nor any part of the study results carried out under this protocol nor any of the information provided by the sponsor to perform the study will be published or passed on to any third party without the consent of the study sponsor.

Any investigator involved with this study is obligated to provide the sponsor with complete test results and all data derived from the study.

Archiving

Investigator File

The study investigator is responsible for maintaining all the records (protocol and protocol amendments, completed source and case report documents, signed informed consent forms, relevant communications, and all other supporting documents) which allow conducting the clinical trial at the site in compliance with ICH-GCP. The study site should retain such documents until at least two years after the last approval of a marketing application or at least two years after the formal discontinuation of clinical development of the investigational product. These documents should be retained for a more extended period if required by the applicable regulatory requirements for the study. Patient identification codes (patient names and corresponding study numbers) will be retained for this same period. The Investigator must contact the Sponsor before disposing of any study records.

Trial Master File

The Sponsor will archive the Trial Master File following ICH-GCP and applicable regulatory requirements.

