- Visit 8 – End of Study, during this final visit (approximately 26 weeks after Week 0), an entire group of study assessments will be performed to evaluate the safety and efficacy of HB-adMSCs (allogeneic) or Placebo administrations.

Clinical assessments of disease activity will take place during the following visits:

- Visit 1 – Screening
- Visit 2 – Infusion 1 → **(Baseline)**
- Visit 3 – Infusion 2
- Visit 4 – Infusion 3
- Visit 5 – Infusion 4
- Visit 6 – Follow Up 1
- Visit 7 – Follow Up 2
- Visit 8 – End of Study

Blood samples for safety evaluations will be obtained at the following visits:

- Visit 1 – Screening. After informed consent has been obtained, laboratory samples will be drawn by venipuncture; the findings of the lab tests will be used to determine whether the individual is eligible for the research.
- Visit 2 – Infusion 1 **(Baseline)**: safety laboratory samples will be drawn by venipuncture to establish a baseline for comparison with the laboratory results obtained in subsequent visits.
- Visit 5 – Infusion 4: safety laboratory samples should be collected by venipuncture during this visit.
- Visit 8 – End of Study: safety laboratory samples should be collected by venipuncture during this visit.

Suppose a study participant receives at least one dose of the experimental drug and decides to withdraw consent after that. In that case, investigators should conduct a safety follow-up visit with this subject's approval to comply with the Sponsor's standard operating procedures.
--

Withdrawal Criteria

In different situations, a study subject may withdraw from the study before the planned completion of the visits. One of these situations is mentioned below,

1. Voluntary withdrawal: the subject doesn't want to continue receiving the investigational product.

The principal investigator and designated staff must record the reason for the subject's withdrawal on the case report forms, specifically in the Early Termination Visit or a Note to File Form.

Study participants discontinued from the clinical trial who received at least one infusion (HBadMSCs - allogeneic or placebo) will be invited to a Safety Follow-up visit.

Any withdrawal must be documented in the source documents and electronic case report forms. If the reason for the discontinuation is an adverse event or serious adverse event, the event must be followed until resolution by the principal investigator.

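### The protocol lists refusal of further infusions as study withdrawal and does not explicitly require Week 26 questionnaires from anyone who stops treatment

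*Protocol*

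**What the plan says.** **Withdrawal Criteria (protocol).** The section opens by saying that "a study subject may withdraw from the study before the planned completion of the visits". It then lists one situation: "Voluntary withdrawal: the subject doesn't want to continue receiving the investigational product". The reason is to be recorded "specifically in the Early Termination Visit or a Note to File Form". Participants discontinued after at least one infusion "will be invited to a Safety Follow-up visit".

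**Infusion Stopping Rules (protocol).** One listed reason to stop an infusion is "The patient verbally declines the treatment at any moment prior, or during the infusion". If an infusion is stopped for an adverse event, no more product is given, and "he or she must be followed for safety purposes according to the protocol".

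**Study Stopping Rules (protocol).** "Should the study participant discontinue study treatment, he/she will be followed for safety according to the protocol safety monitoring plan". The next sentence adds: "The study participant will receive follow-up communication via phone calls or electronically to ascertain the outcome until resolved fully". The section ends by keeping all participants under follow-up to End of Study, but ties this to the study being stopped or suspended.

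**Table 1 and Visit 8 (protocol).** VAS, FAS and PHQ-9 are scheduled at Weeks 0, 2, 6, 10 and 26, and SF-36 at Weeks 0, 10 and 26. Weeks 14 and 20 are telephone calls without questionnaires. Neither the Early Termination Visit nor the Safety Follow-up visit has a column or a list of assessments.

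**SAP.** The primary endpoint is change in neurological VAS from baseline to Week 26 (section 5.2.2). The efficacy analysis set admits only participants who received all four infusions (section 4).

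**The concern.** Stopping the product and leaving follow-up are different events. A participant may decline another infusion and still be willing to fill in a questionnaire at Week 26, which needs no infusion. Where a protocol treats the first event as the second, the primary outcome of a willing participant can be lost for an administrative reason.

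Week 26 is the only efficacy assessment after the treatment period, so a lost Visit 8 has no later substitute. Stopping is foreseeable here because the infusion rules list many triggers and bar further product after a stop for an adverse event. If stoppers differ from completers, and stopping differs between arms, a comparison without them is not the randomized comparison. An analysis set can be redefined before unblinding, but a score that was not taken cannot be recovered.

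**Working it through.** The documents give no stopping rate, SD or power statement, so there is no planned figure to reproduce. The check is mainly a comparison of texts, followed by an illustration on assumed inputs.

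**1. The routes side by side**

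| Route | Where | Follow-up stated | Week 26 questionnaires explicitly required? |
|---|---|---|---|
| Does not want more product | Withdrawal Criteria | Invitation to a safety visit; no date or content | No |
| Withdraws consent after at least one dose | Investigational Plan, last paragraph | Safety visit if the participant agrees | No |
| Infusion stopped for an adverse event | Infusion Stopping Rules | Safety follow-up under the protocol | Not stated; can be read as keeping Visit 8 |
| Discontinues study treatment | Study Stopping Rules | Safety monitoring plan; telephone or electronic contact | No |
| Whole study stopped or suspended | Study Stopping Rules | Everyone to End of Study | Yes, through Visit 8 |

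The first two rows lead to much the same place, although only the second is a refusal of follow-up. The individual who stops treatment has no sentence matching the last row. The calls at Visits 6 and 7 are described as being for active participants.

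**2. One participant followed through.** A participant declines infusion 3 at Week 6 and is handled under Withdrawal Criteria. The last scheduled VAS is then at Week 6 at best, which is 26 − 6 = 20 weeks before the primary time point. The only scheduled SF-36 is the one at Week 0.

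**3. Precision, if Week 26 scores are missing equally in both arms.** With 80 participants randomized 1:1 (SAP sections 6 and 2.2), n = 80/2 = 40 per arm. Two-sided alpha is 0.05 (SAP section 5.1.1). Using the normal approximation, the standardized difference detectable with 80% power is (1.960 + 0.842) × √(2/n). Power is then evaluated at a true difference of 0.626 SD, the value detectable at n = 40.

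| Assumed stopping | n per arm | Detectable difference (SD) | Power at 0.626 SD |
|---|---|---|---|
| 0% | 40 | 0.626 | 79.9% |
| 5% | 38 | 0.643 | 77.9% |
| 10% | 36 | 0.660 | 75.7% |
| 20% | 32 | 0.700 | 70.7% |
| 25% | 30 | 0.723 | 67.9% |

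**4. Bias, if stopping is unequal.** If a fraction p of an arm stops and stoppers do worse than completers by d, the completers' mean overstates that arm's result by p × d. The comparison shifts in favour of the active arm by pA × dA − pP × dP.

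- Stopping in one arm only: 0.05 × 0.5 = 0.025 SD; 0.05 × 1.0 = 0.05 SD; 0.20 × 0.5 = 0.10 SD; 0.20 × 1.0 = 0.20 SD.
- In centimetres, with the same d in both arms: (0.10 − 0.025) × 2 = 0.15 cm; (0.20 − 0.05) × 3 = 0.45 cm. Exchanging the arms in the last case gives (0.05 − 0.20) × 3 = −0.45 cm.

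All rates and values of d are assumptions, and the sign follows from which arm stops more.

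**5. What collection alone would change.** The SAP efficacy set excludes anyone with fewer than four infusions, so the figures in steps 3 and 4 apply to the planned primary analysis whether or not stoppers attend Visit 8. Collecting the scores and admitting them to the analysis are both needed.

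**The case against.** A reader might infer that stoppers' Week 26 scores are never collected, or are missing by design. The documents do not say so. Nothing forbids collection. The Investigational Plan expects each consented participant to complete the visits, Visit 8 carries the full set of assessments, and Table 1 makes no exception for people off treatment.

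A reader might also infer that those stopped for an adverse event are lost. The text points, if anything, the other way. Their safety follow-up is to be according to the protocol, whose primary safety endpoints run to Week 26 and are measured at Visit 8, where all four questionnaires are completed. PHQ-9 is itself listed under a safety objective. The safety monitoring plan is not described here and may ask for more than telephone contact.

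Third, refusal of product is introduced as one of several situations, so it is not a complete definition of withdrawal. Declining a single infusion, as in the Infusion Stopping Rules, can differ from not wanting to continue, and that list sets no follow-up rule for a refusal. A contradiction between those two places is not shown.

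Finally, a bias in favour of the cells is tempting to infer, but no reasons or rates by arm are given. The SAP's 1.9 threshold is no yardstick for it: it is a pain-VAS value applied to mean change from baseline, not to a difference between arms.

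These points stand and limit the claim. They do not remove the gap: voluntary refusal is listed as leaving the study, the two off-schedule visits have no content, and no sentence explicitly asks an individual stopper for Week 26 questionnaires.

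**Conclusion.** The concern holds as a gap in what the protocol requires, not as a demonstrated loss of data. Followed as written, the Withdrawal Criteria are likely to lose the Week 26 outcome of voluntary stoppers who would have been willing to give it. For those stopped because of an adverse event, the outcome depends on how staff read the safety follow-up wording.

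The size and direction of any effect on the treatment comparison are unknown. The illustrative range of 0.025 to 0.20 SD, and the fall in power from 79.9% to 75.7% at 10% stopping or 70.7% at 20%, rest entirely on assumed inputs. They describe an analysis without stoppers, which the SAP's efficacy set would produce in any case. This is an inexpensive improvement worth making, and its benefit for efficacy depends on changing that set too.

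**What to change.** **Protocol.** In Withdrawal Criteria and in the follow-up paragraphs of the Infusion and Study Stopping Rules:

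- Separate stopping study treatment from withdrawing consent for follow-up.
- State that participants who stop treatment for any reason are asked to complete the remaining scheduled assessments, at minimum the Visit 8 questionnaires and safety assessments, unless they withdraw consent.
- Give the Early Termination Visit a defined content, with VAS, FAS, SF-36 and PHQ-9 collected if a withdrawing participant agrees.
- Record the two statuses and their dates separately in the CRF.
- Reconcile the follow-up wording across these sections. No infusion or study stopping criterion needs to change for this.

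**SAP.** Redefine the efficacy set in section 4 as all randomized participants who received at least one infusion, analysed as randomized. This would also agree with the protocol's Statistical Methods, which promise to analyse all data from enrolled and dosed participants.

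**Cost.** The visit and forms already exist. The change needs a protocol amendment with FDA and IRB agreement, an SAP revision, a small CRF change and a few more Visit 8 attendances. Some stoppers may still decline, so some missing Week 26 scores will remain.
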